In the adjuvant setting, sterilizing microscopic disease potentially persistent after radical surgery, particularly in high-risk patients, represents the rationale of adding WPRT to prostatic bed radiotherapy in pN0 patients. Goldner et al. evaluated the clinical impact of prostate only adjuvant RT in pN0 patients showing a 5-year biochemical relapse free survival of 100% and 58% in patients with a risk of nodal involvement <15% and >15%, respectively. These findings may be explained by a microscopic involvement of pelvic structures (lymph nodes, bone) other than prostate bed. However, the role of adjuvant post-surgical WPRT need to be validated by large prospective studies, not actually ongoing to our knowledge. [37, 38, 39, 40]. Moreover, no clear-cut guidelines are available about the usefulness of adding ADT to adjuvant RT in the different subsets of pN0 patients.

On the other hand, nodal involvement (pN1) is a strong negative prognostic factor and adjuvant RT in these patients may be useful to optimize loco-regional control deferring first or second line systemic therapies [41]. Actually, the standard adjuvant treatment for pN1 PCa patients is represented by long term ADT, but the association with WPRT might significantly increase survival outcomes [42]. A recent analysis conducted by SEER on “pN1 M0” PCa patients treated with adjuvant WPRT seems to confirm the benefit obtained by the association of WPRT with ADT, demonstrating a survival advantage for intermediate risk patients [43].

Conclusions, rationale and summary of the study

In conclusion, open questions about ENI for prostate cancer still remain:

1. In the exclusive radiotherapy scenario, does ENI produce an overall or biochemical relapse free survival advantage over prostate only radiotherapy for intermediate/high/very high risk cases?
2. If ADT is added to prostate only radiotherapy, in intermediate/high/very high risk cases, ENI is any longer needed?

3. Is ENI, associated or not to ADT, linked with an OS or bRFS survival advantage in patients submitted to adjuvant postsurgical prostate radiotherapy?
4. Additional toxicity due to the larger volumes treated might be reduced by more sophisticated radiotherapy techniques when ENI is added to prostate?
5. How many Radiation Oncology centers use ENI to treat patients with intermediate/high/very high-risk prostate cancer, with or without ADT?

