We propose a no-profit, multicenter observational study to collect data of consecutive patients treated with ENI both in the exclusive radical radiotherapy scenario and in the adjuvant postsurgical setting. Cases treated both with and without associated ADT will be recruited to evaluate Overall survival (OS) (that will be the main endpoint), Cause-specific (CSS) and Biochemical Relapse Free survival (bRFS), toxicity and Quality of Life (QoL) (the secondary endpoints).

Aims of the study

Clinical features and outcomes will be assessed as better detailed in the following lines:

1. To define the diffusion of the practice of treating pelvic lymph-nodes in patients affected by intermediate/high/very high risk non-metastatic prostate cancer (PCa) among Italian Radiation Oncology Centres, submitted to radical or post-operative radiotherapy;
2. To define the diffusion of the different radiotherapy techniques used to treat pelvic nodes and the other features of the radiation treatment;
3. To register prospectively biochemical and clinical failure, prostate cancer deaths and deaths for any cause in the population studied;
4. To register prospectively the toxicity due to radiotherapy and androgen deprivation therapy in patients treated with pelvic nodes radiotherapy;
5. To compare clinical outcomes and toxicities observed in the different clinical and therapeutic subgroups with the corresponding historical data relative to PCa patients treated with radiotherapy with or without elective pelvic nodal irradiation, already available in the existing AIRO (Italian Society of Radiation Oncology) databases;

6. To exploit the collected data to define the need and the features of a prospective randomized trial evaluating the efficacy of elective pelvic nodal irradiation in patients with intermediate/high/very high risk non-metastatic prostate cancer.
7. The data obtained from the present observational study will be helpful for designing a subsequent randomized controlled trial.

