In summary, the study aims at the definition of survival, toxicity and QoL data in a representative sample of intermediate, high and very high risk prostate cancer patients consecutively recruited in Italian Radiation Oncology Centres over two years. Parameters considered will be OS, CSS and bRFS, toxicity (rectal, bladder, bowel toxicity, according to CTCAE v.4 scale) and QoL (according to the SF-12 scale and UCLA-PCI scale). Primary end point will be OS. Secondary endpoints will be CSS, bRFS, gastrointestinal and genitourinary toxicity, QoL deterioration.

Study Design

This is a prospective, multicenter, observational cohort study aimed to describe the advantage/disadvantage of different treatments of patients with intermediate/high/very high risk prostate cancer, through a web-based database.

Study Duration

The recruitment period, taking into account the needed sample size (*v.infra*) will be of two years, followed by three-year follow up period for each patient, with an accrual of at least 400-500 patients.

Population, Procedures

The study will include all consecutive patients affected by intermediate, high or very high-risk prostate cancer that fit the inclusion criteria and who are evaluated at each Centre involved in the study. Patients may have already undergone or not to radical prostatectomy and/or pelvic lymphadenectomy.

Inclusion criteria

- Men older than or aged 18 years;
- Histologically confirmed intermediate, high or very high risk prostate cancer patients (NCCN classification: Intermediate Risk T2b and T2c or Gleason Score 7 or PSA value between 10 and 20 ng/mL; High risk: T3a or Gleason score 8-10 or PSA > 20 ng/ml; Very high risk: T3b-T4 or patients with multiple adverse risk factors reported in the high risk category that may be shifted in the very high risk group
- Patients eligible for -and actually submitted to- radical radiotherapy treatment (+/- androgen deprivation) or adjuvant radiotherapy treatment after surgery (radical prostatectomy +/- pelvic lymphadenectomy);
- No other synchronous or previous malignant tumor other than skin basal cell carcinoma;
- Patients able to understand and sign the appropriate informed consent;
- Patients able to fill the QoL questionnaire;

Exclusion criteria

- Patients aged less than 18;

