- Patients not eligible for -and actually not submitted to- radical radiotherapy treatment (+/- androgen deprivation) or adjuvant radiotherapy treatment after surgery (radical prostatectomy +/- pelvic lymphadenectomy);
- Low risk prostate cancer (<T2b and T2c or < Gleason Score 7 or PSA value < 10 ng/mL);
- Patients with synchronous or previous malignancy other than skin basal cell carcinoma;
- Patients able to understand and sign the appropriate informed consent (IC) who decide not to subscribe IC;
- Patients not able to understand and sign the appropriate informed consent (IC)

- Patients unable to fill the QoL questionnaire.

Involved Centers

The Radiation Oncology Unit of the University and Spedali Civili of Brescia will be the promoter and coordinator Center. From previous studies of the AIRO Prostate Study Group it can be inferred that at least 15-20 Radiation Oncology Centers from different areas of Italy will be involved; this will assure the widest and homogenous participation throughout the country.

Accrual and timeline

The study will start when a sufficient number of Centres will have obtained EC approval.

Estimated total time of recruitment is 2 years. It will be followed by a three years period of follow up for each patient.

Phase 1: Establishment of the network of Centers involved in the study

During this phase the study protocol has to be shared as much as possible within the Italian radiation oncology community in order to identify and involve as many as possible interested Centres throughout the country.

This will be done in official sessions of the Prostate Cancer Study Group (PCSG) of AIRO meetings.

Each center that will become a part of the study will identify a referring physician who must accomplish the systematic recruitment of eligible patients and provide the collection of data on the appropriate *web portal* established in Brescia.

Phase 2: Activation and recruitment of eligible cases

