	2 . Yes, monolateral
	3 . Yes, bilateral
Pathological TNM after surgery	T __ N __ M __
Margins	1 R0
	2 R1
	3 R2
Gleason Score after surgery	__ + __ = __
Pre-treatment PSA __ ng/mL	
PSA date	__ / __ / __ day month year

SF-12 STANDARD ITALIAN VERSION

(Apolone G et al. 2001)

	Excellent	Very good	Good	Fair	Poor
1 In general, you would say that your health condition is:	1	2	3	4	5
The following questions regard some activities you might do during a typical day. Does your health condition actually limit you in doing these activities?					
	Yes, it limits a lot	Yes, it limits a little	No, it does not limit at all		
2 Activities of moderate physical effort , such as moving a table , using the vacuum cleaner , playing bowls or a riding a bicycle	1	2	3		
3 Climbing several flights of stairs	1	2	3		
During the last 4 weeks have you had the following problems at work or during other daily activities, because of your physical health condition?					
	Yes	No			
4 Accomplished less than you would like	1	2			
5 You had to limit certain kinds of occupation or other activities	1	2			
During the last 4 weeks have you had the following problems at work or during other daily activities, because of your emotional state (such as feeling depressed or anxious)?					
	Yes	No			
6 Accomplished less than you would like	1	2			
7 You did not do work or other activities as carefully as usual	1	2			
	Not at all	A little bit	Moderately	Quite a bit	Not at all
8 During the last 4 weeks , How much has pain hindered your usual work (at home and outside)?	1	2	3	4	5
How long during the last 4 weeks have you felt					
	All of the time	Most of the time	A good bit of time	Some of the time	A little of the time
9 calm and serene?	1	2	3	4	5
10 full of energy?	1	2	3	4	5
11 discouraged and sad	1	2	3	4	5
	All of the time	Most of the time	A good bit of time	Some of the time	A little of the time
12 During the last 4 weeks , how long have your physical health condition or your emotional state interfered with your social activities, with family, with friends?	1	2	3	4	5

COMPLICATIONS DUE TO PROSTATE CANCER
ITALIAN UCLA PROSTATE CANCER INDEX
(Gacci M et al, 2005)

URINARY FUNCTION

This session regards the urinary routine. Please consider only the last 4 weeks.

1. Over the LAST 4 WEEKS, how often have you leaked urine?
 - 1 Every day.
 - 2 About once a week
 - 3 Less than once a week
 - 4 Not at all.

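### Eligibility omits M0, and neither eligibility nor analysis separates N0 from N1 men, so the unstratified survival comparison of elective nodal irradiation is open to confounding by nodal status

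*Combined protocol and SAP*

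**What the plan says.** **Aims.** Aims of the study, item 1, is about how widely pelvic nodes are treated in "intermediate/high/very high risk non-metastatic prostate cancer (PCa) among Italian Radiation Oncology Centres". Item 6 looks ahead to a randomised trial "evaluating the efficacy of elective pelvic nodal irradiation in patients with intermediate/high/very high risk non-metastatic prostate cancer".

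**Eligibility.** The inclusion and exclusion lists, in the synopsis and under Population, Procedures, grade risk by T stage, Gleason score and PSA. The top category reads "Very high risk: T3b-T4 or patients with multiple adverse risk factors reported in the high risk category". The treatment criterion admits radical radiotherapy or "adjuvant radiotherapy treatment after surgery (radical prostatectomy +/- pelvic lymphadenectomy". The study population paragraph adds "Patients may have already undergone or not to radical prostatectomy and/or pelvic lymphadenectomy". The only disease-extent exclusion is at the low end: "Low risk prostate cancer (<T2b and T2c or < Gleason Score 7 or PSA value < 10 ng/mL". No line mentions N or M.

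**Background.** The section on postoperative treatment gives the elective rationale, sterilising microscopic disease, for pN0 men. It then says that "nodal involvement (pN1) is a strong negative prognostic factor", names long-term androgen deprivation as the standard adjuvant treatment in that group, and says that adding whole-pelvis radiotherapy might improve survival.

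**Analysis.** Statistical Analyses plans Kaplan-Meier curves and log-rank tests between groups, with no stratification factor. It also plans regression on some variables, allowing for confounders that it does not name. It does not define the ENI group.

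**Forms.** Attachment 1 records clinical TNM, numbers of removed and positive nodes, and "Pathological TNM after surgery". Attachment 2 codes the target volume as including the pelvis or not, without separating elective from therapeutic nodal treatment.

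**The concern.** Open questions 1 to 3 in the rationale ask whether ENI improves overall or biochemical relapse-free survival. Elective treatment presupposes nodes not known to be involved. If pelvic radiotherapy alone defines the ENI group, a man with positive nodes counts as ENI by default.

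The background supplies both ingredients of confounding by indication: N1 men have a worse prognosis, and there is a stated reason to irradiate the pelvis in them. If they gather in the pelvic-radiotherapy group, a crude comparison makes ENI look worse than it is. Aims 6 and 7 use these results to judge the need for a randomised trial and to design it, so the distortion would carry forward. Aim 5, the comparison with historical data with or without elective nodal irradiation, has the same weakness.

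**Working it through.** **The plan's own figure.** Sample size states a 95% interval of 0.76 to 0.84 for a 5-year survival of 0.80 with 400 patients. The Wald formula gives 0.80 ± 1.96 × √(0.8 × 0.2/400) = 0.761 to 0.839, which agrees. This concerns one overall estimate, so the present point does not affect it.

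**Inputs.** The documents give 400 patients, 5-year survival of 0.80 and 3 years of follow-up per patient. They give no N1 share, N1 hazard ratio or ENI split. The following are assumptions:
- exponential survival, with the 0.80 applied to N0 men;
- no true ENI effect;
- N1 hazard ratio H of 2 (range 1.5 to 3).

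**Formulas.** Baseline hazard h = −ln(0.80)/5 = 0.0446 per year. If a share q of a group is N1, then S(T) = (1 − q)·exp(−hT) + q·exp(−H·h·T). The crude hazard ratio is approximated by ln S(ENI)/ln S(no ENI).

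**Main scenario.** 10% of the cohort is N1, all of them receive pelvic radiotherapy, and H = 2. At 5 years N0 survival is 0.80 and N1 survival is 0.80² = 0.64.
- 50% receive pelvic radiotherapy: q = 0.10/0.50 = 0.20. S(ENI) = 0.8 × 0.80 + 0.2 × 0.64 = 0.768 against 0.800, a difference of 3.2 points. Hazard ratio = ln 0.768/ln 0.800 = 1.18.
- 30% receive pelvic radiotherapy: q = 0.10/0.30 = 0.333. S(ENI) = 0.747 against 0.800, a difference of 5.3 points. Hazard ratio = 1.31.
- At 3 years, the planned follow-up, the first case is 0.853 against 0.875: 2.2 points, hazard ratio 1.19.

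**Grid.** N1 share in the ENI group against the other group, with 200 men in each; 5-year crude hazard ratio:

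| N1 share | H = 1.5 | H = 2 | H = 3 |
|---|---|---|---|
| 10% vs 0% | 1.05 | 1.09 | 1.16 |
| 20% vs 0% | 1.10 | 1.18 | 1.33 |
| 20% vs 5% | 1.07 | 1.13 | 1.23 |
| 30% vs 0% | 1.14 | 1.28 | 1.51 |
| 30% vs 5% | 1.12 | 1.22 | 1.40 |

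The 5-year differences run from 0.8 to 8.6 points (0.6 to 6.2 at 3 years). With no ENI effect, a nominal 5% two-sided log-rank test rejects in about 5.5% to 53% of studies at 5 years and 5.3% to 41% at 3 years. The weaker contrast of 10% against 5% at H = 1.5 gives ln 0.7916/ln 0.7958 = 1.02, so the low end is close to no bias.

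**Against sampling error.** In the main scenario with 200 per group, about 55 deaths are expected by 3 years. The standard error of the log hazard ratio is then about 2/√55 = 0.27. The bias is ln 1.19 = 0.17, or about 0.6 of a standard error.

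**Effect of handling N.** If every N1 man receives pelvic radiotherapy, the N1 stratum has no comparator and contributes nothing to a stratified log-rank test. The result rests on N0 men and the modelled hazard ratio is 1.00. Simulating the main scenario gave a crude hazard ratio of 1.19, and 1.01 with N either as a covariate or as a stratum.

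**The case against.** The strongest reply is that the plan already holds the remedy. TNM and positive nodes are collected, regression allowing for confounders is planned, and adjustment for N works. A reader might infer that adjustment must fail because N1 men without pelvic radiotherapy are scarce. That is wrong: without comparators the N1 men simply stop contributing, and the N0 men supply the estimate. What remains is that N is not named and the log-rank comparison is not stratified.

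A reader might also take the loading and the bias as established. The documents do not support that. They describe whole-pelvis radiotherapy in pN1 only as possibly beneficial and give none of the three quantities needed. Assumptions can be chosen that give a crude hazard ratio of 2.23, but only at 20% N1, 30% pelvic radiotherapy and H = 3, which makes two-thirds of the ENI group N1.

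Nor does enrolling N1 men contradict the non-metastatic aims. The background itself refers to pN1 M0 patients and discusses them under an elective-irradiation heading, so their entry into a consecutive cohort may be deliberate. M1 entry is already limited by implication, since treatment must be radical or adjuvant. The M0 line therefore aligns wording, and no M1 effect has been quantified.

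Finally, the sample size rests on one survival estimate and the study is largely descriptive. That limits how much weight any ENI contrast can bear. It does not remove the point, because the rationale asks about a survival advantage and group log-rank tests are planned.

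**Conclusion.** The point holds in a bounded form. Eligibility does not state the non-metastatic restriction in aims 1 and 6, and nothing in eligibility or analysis separates N0 from N1 when ENI is assessed. If N1 men are over-represented among those given pelvic radiotherapy, which the background makes likely, the unstratified overall survival comparison is biased against ENI.

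The size is conditional. The crude hazard ratio is about 1.18 or 1.31 in the main scenario, depending on the pelvic-radiotherapy share, and 1.05 to 1.51 over the tabulated grid. It approaches 1 if N1 men are only slightly more common in the ENI group. All of this assumes exponential survival, no true ENI effect and 5-year survival of 0.80 in N0 men.

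The direction applies to overall survival only. For biochemical relapse-free survival it is uncertain, because long-term androgen deprivation, the stated standard in pN1, could delay PSA failure within a 3-year follow-up.

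The sponsor should make the change. The bias is avoidable with data already collected.

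**What to change.** - **Eligibility:** reconcile the lists with aims 1 and 6 by stating M0. Keep N1 men enrolled, which preserves consecutive recruitment.
- **Analysis set:** define elective irradiation for analysis, and compare ENI with no ENI in N0 men, meaning pN0, or cN0 where nodes were not assessed pathologically. Alternatively, stratify the log-rank test and regression by N status, which also removes the modelled bias. If some N1 men do not receive pelvic radiotherapy, the stratified result includes their contrast too, so the plan should say which comparison is primary.
- **N1 men:** report them as a separate descriptive stratum.

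**Cost:** one eligibility line and one analysis-set definition, with no new data items. The comparison set shrinks slightly. In the main scenario with 50% pelvic radiotherapy, 360 of 400 men remain (160 against 200). Expected N0 deaths by 3 years are 360 × 0.125 = 45, about 20 and 25. The standard error of the log hazard ratio rises from 0.27 to √(1/20 + 1/25) = 0.30.
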